**Faculty of Physical Therapy**

**Kafrelsheikh University**

**2022/1444**

# CHAPTER I

## INTRODUCTION

Cerebral palsy (CP) is a nonprogressive motor impairment syndrome caused by brain defects or lesions that occur in an immature brain before or during birth or within two years of birth (1).

It is accompanied by motor disorder; disturbances of sensation, cognition, perception, communication, and behaviour; and seizure disorder and affects overall development (2,3).

Accordingly, children with CP show reduced postural control when engaging in several activities such as sitting, standing, and walking and have limitations in performing the activities of daily living (4,5).

Therapeutic approaches for CP include neurodevelopmental treatment, Vojta therapy, sensory integration therapy, and conductive education. Specific therapeutic strategies for CP may differ, but they all aim to improve the independence of children with CP (6).

Considering that the rehabilitation period of patients with CP is observed in a prolonged period of time, it is important to induce the sustained participation of these patients, making sure that the therapeutic interventions are interesting and easily performed (7). For this we will use this treatment tools in our study.

Spider therapy is an intensive treatment approach which was originally developed in Poland. It involves suspending the child in the Centre of universal exercise unit by using a number of elastic bungee cords of different elasticity, these cords are attached to specific points on special belt around the child's waist, forming a unique spider web around the child which provides them essential support (8).

Virtual reality gaming augments a desirable motor processing skills through task-driven training and also encourage problem-solving. With a higher

concentration and engagement of goal-driven games, the virtual reality gaming might influence the cognitive-motor planning of children with CP (9).

In the past, traditional neurophysiological approaches and novel emerging rehabilitation strategies addressed the gross motor function and balance capacity of children with CP (10).

Recommended that the group therapy, goal-directed motor practice, strengthening exercises, treadmill training, balance and walking training were beneficial for functional mobility of children with CP. In recent times, technological advancement has gained momentum in developing strategies for limb recovery and balance capacity of the paediatric and adult population with brain dysfunction (11).

## **Statement of the Problem**

This study will be conducted to answer the following research question: Is there any significant effect of virtual reality and physiotherapy in spider cage on gross motor performance and balance in children with spastic diplegia?

## **Purpose of the Study**

This study will detect the effect of virtual reality in spider cage on gross motor performance and balance in children with spastic diplegia.

## **Significance of the Study**

The current study will be directed to investigate effect of virtual reality on gross motor and balance as the weakness of the trunk muscles and lower limb muscles along with spasticity potentially predispose balance and walking issues of children with bilateral spastic CP (12).

The balance deficits in children with CP are multifactorial. According to the system's model proposed by Woollacott and Shumway-Cook, multiple

systems contribute to postural dysfunction in children with CP. Muscle weakness and stiffness of lower limb muscles account for biomechanical constraints and postural malalignment during standing and functional balancing (13).

Virtual reality is one of the novel technology-based approaches to treat balance and motor function in children with CP. It utilizes the interactive simulations created in computer hardware and software, in which the children find opportunities to engage in environments appearing real to them (14).

After reviewing the available previous published studies, it was found that there is no previous study directly compared between the effects of virtual reality and physical therapy in spider cage on gross motor performance and balance with diplegic children CP children. Both therapeutic modalities were found to induce good clinical outcomes when studied separately, so this study will be conducted to examine the effectiveness of virtual reality.

The greater demand for physical therapy for Paediatrics' signifies the need for more effective, safer and evident therapeutic modalities. The findings of this study will help both; the therapists and the children to save time, effort and reach the best results in concise times.

## **Delimitations**

This study will be delimited to:

- 30 children with spastic diplegia with age range from 6 to 12 years are enrolled in the study.
- Children will be randomly allocated into two equal groups; Group A will receive virtual reality and physiotherapy, while Group (B) will receive physiotherapy alone.
- All children will receive three sessions per week for twelve weeks.
- Variables will be evaluated pre and post treatment for all child.

- Gross motor performance will be evaluated using Gross Motor Function Measure 88 (GMFM-88).
- Balance will be evaluated using Pediatric Balance Scale (PBS).

## **Hypotheses**

This study will test the following hypothesis:

There will be no significant the effects of virtual reality on gross motor performance and balance in children with spastic diplegia.

## **Basic Assumptions**

It will be assumed that:

1. Assessment tools are valid and reliable.
2. The participants will be cooperative during evaluation and treatment.
3. All children will recognize and follow verbal order included in both testing and training techniques.
4. Both genders will participate in the study.

## **CHAPTER II**

### **LITERATURE REVIEW**

The goal of the study is to see effect of virtual reality and physiotherapy in spider cage on gross motor performance and balance with diplegic children. This study reviews the following related titles as follows:

- 1. Cerebral palsy.**
- 2. Spastic diplegia.**
- 3. Virtual reality.**
- 4. Gross motor performance.**
- 5. Balance.**
- 6. Gross Motor Function Measure 88 (GMFM-88).**
- 7. Pediatric Balance Scale (PBS).**

#### **1. Cerebral palsy**

##### **A. Definition**

Cerebral palsy (CP) refers to a group of disorders caused by faulty development or damage to motor areas in the brain that disrupts the brain's ability to control movement and posture (15).

Cerebral palsy refers to a group of posture and movement disorders occurring as a result of a non-progressive lesion of the developing central nervous system. This damage to the immature brain leads to problems with balance, coordination, and movement (16).

Cerebral palsy is a motor impairment syndrome, which is a result of non-progressive insults or anomalies in the early brain development period (17).

## **B. Etiology of Cerebral palsy**

### **Prenatal period:**

Prenatal period causes may be viral infections, radiation exposure, congenital brain malformation, problem of placental malfunctioning and maternal disorder (18).

### **Perinatal period:**

Perinatal period causes may be pre-eclampsia, asphyxia or anoxia, trauma, intra-ventricular hemorrhage and respiratory disorders of prematurity, neonatal causes are infection, acute metabolic disorders and blood incompatibility (18).

### **Post-natal period:**

Postnatal causes include head injury, infection, viral and bacterial meningitis, encephalitis, cardiovascular accident, malnutrition and toxins (14). Post-natal causes may be traumatic head injury, viral and bacterial meningitis, anoxia and toxins (18).

## **C. Classifications**

Spastic-type CP is the most common type, comprising 85%-91% of all CP cases. Dyskinetic CP, which includes athetosis and dystonia, comprises 4%-7% of cases, whereas ataxic CP and hypotonic CP constitute 4%-6% and 2%, respectively (19). Spastic CP is further sub-classified into hemiplegia (38% of all spastic CP cases), diplegia (37%), and quadriplegia (constituting 24%). Thus, out of all the subtypes, hemiplegia is the most widely seen presentation in children with CP (19).

## **2. Spastic diplegia.**

Children with spastic Cerebral Palsy (CP) have smaller and weaker muscles than healthy children. Muscle strength correlates with gait and motor

function and strength is more highly related to function than spasticity. Spastic muscles respond positively to strength training and strength gains have been shown to be similar or greater than those reported in the healthy population (20). Various studies have reported significant improvements in gait following strengthening programmes in terms of temporal parameters and Gross Motor Function Measure (GMFM) Dimension E (21).

McPhail and Kramer found a direct correlation between the strength gained and functional improvement, but significant changes in gait kinematics following strength training appear difficult to achieve and have rarely been reported (22).

These strengthening studies, however, presume weakness is present, and reports specifically documenting the extent and distribution of muscle weakness in children with CP remain very limited. In Spastic Diplegia (SD), the most prevalent diagnostic category of CP, muscle strength has been quantified at the knee joint, and two lower limb strength profiles have been undertaken and compared with controls (23).

### **3. Virtual reality (VR).**

Virtual reality is one of the novel technology-based approaches to treat balance and motor function in children with CP. It utilizes the interactive simulations created in computer hardware and software, in which the children find opportunities to engage in environments appearing real to them (24).

The children get constant feedback about the movement and posture of their body in virtually immersive and non-immersive conditions that are conducive to motor learning (25).

VR is reported to augment the desirable motor performance because of brain plasticity and brain reorganization through active participation, receiving feedback, and repetition of movements (26).

VR increases the exercise compliance level in achieving selective motor control and enhances conventional physiotherapy effectiveness (27).

Luna-Oliva et al showed improvement in the motor and processing skills, balance, gait speed, running, jumping, and manual dexterity in children with CP after 8 weeks of VR intervention. VR combined with physiotherapy appears to be a promising new treatment approach with wider future applications. Research over the past decade using VR intervention has reported benefits to children with CP. VR may assist children in acquiring new motor skills, sustaining the benefits from exercise, and enabling children to use their hands for more functional skills. If this is indeed, the case the combined approach may have the potential to greatly enhance the abilities of the child, improving independence alongside minimizing secondary implications associated with growth and development (28).

#### **4.Gross motor performance.**

The impairment in CP, including secondary impairments such as spasticity, muscle contracture, bone deformity, muscle weakness, and coordination disorders, is multifactorial and primarily affects the lower extremities, such as deficits in walking ability (29).

The varying levels of impairment affecting children with CP can be described according to the Gross Motor Classification System. Physical inactivity in children with CP increases the risks of secondary problems such as pain, depression, social isolation, fatigue, pressure sores, and mobility limitations. Children with CP suffer from motor and cognitive disabilities, which usually require a long-term, multifaceted, and multidisciplinary approach (30).

Children with CP also tend to have lower endurance, muscular strength, and cardiorespiratory fitness than the general population. The consequences of chronic muscle imbalance and the resultant deformities can cause increasing disability with age. One of the most significant problems faced by children with

CP is defective postural control. Maintaining postural control, which is required to perform activities of daily living, is often a major challenge for children with CP (31).

## **5.Balance.**

Spastic diplegia, the most prevalent type of CP, is characterized by a wide range of ambulatory outcomes. It affects bilateral lower extremities more than upper extremities in most cases. As a result, walking function and corresponding balance control are impacted (32).

Balance control is important in the performance of most functional skills. Postural balance control in children with CP deteriorates as compared to typically developing children, most likely due to slowed and impaired development of neural motor control mechanisms together with the common secondary musculoskeletal abnormalities (33).

Balance control plays a central role in the motor dysfunction in children with spastic diplegic cerebral palsy. Reduced ability of children with spastic diplegia to adapt the sensory and motor components of postural control to changing task and environmental demands affects their proper response to balance disturbance, the recovery from unexpected threats to stability that refer to reactive balance control, functional deficits and the subsequent limitations in mobility. The amount of time required to recover stability following a balance threat (time of stabilization) and the mean area of centre of mass (COM) displacement per second during balance recovery are increased in these children (34).

Due to poor postural control, the delineation “walking by falling” is especially true for children with CP. A heightened fear of falling can also lead to restriction of activities. Although not all falls can be prevented, those due to poor postural control can be reduced by improving balance performance (35).

Falls may result in pain, injury and disability, and individuals may lose confidence in their ability to perform routine activities. Because a relation has been established between constraints on balance control and functional limitations in children with CP, increased efficiency of postural balance control may be necessary for them to facilitate functional performance (36).

Therefore, many researchers have suggested that balance training should be a crucial component of any rehabilitation program for these children. Such training can modify postural balance control by modulating the amplitude of muscle activities and speeding recruitment of the postural muscles (37).

While there are many easy-to-use functional scales for assessing posture balance control, advanced laboratory systems provide more detailed information on both static and dynamic balance. The balance platform is commonly employed in balance analysis laboratories for assessing postural balance with regard to oscillations from the centre of pressure in the anterior-posterior and medial-lateral directions (38).

## **6. Gross Motor Function Measure 88 (GMFM-88).**

The GMFM is used by a variety of rehabilitation specialists for clinical and research purposes to measure change over time, and the effectiveness of interventions to affect change (39).

The standardized measures provide objective information in an easy-to-understand format. As stated earlier, the GMFM has become the standard tool for measuring change in gross motor function over time for children with CP. Given its unique purpose, its wide use, and the amount of research that has been conducted using this outcome measure, examining the usefulness as related to intervention is important to measure change over time for children with CP. The Gross Motor Function Measure (GMFM) and its subsequent revisions, has become the most common functional outcome measure used by rehabilitation specialists to measure gross motor functioning in children with CP and other

neurologically based conditions, such as Down syndrome and traumatic brain injury (40).

This tool showed high validity at 0.91 when applied, the GMFM-88 was reported to be a useful method for measuring gross motor function in children with CP because of its high reliability, with inter-rater reliability of 0.77, test–retest reliability of 0.88, and intra-rater reliability of 0.68 (41).

## **7. Pediatric Balance Scale (PBS).**

The PBS is a standardized tool for testing balance. this tool developed by modifying the Berg Balance Scale to test the functional balance of the school-age population with mild-to-moderate motor impairment. The tool has been confirmed to be reliable in terms of both intra-rater reliability (intraclass correlation coefficient (ICC) = 0.99) and inter-rater reliability (ICC = 0.99). The items can be measured within 15 min and do not require the use of specialized equipment (42).

## **CHAPTER III**

### **SUBJECTS, MATERIALS, AND PROCEDURES**

#### **I. Subjects**

The current study will target children with spastic diplegia. Patients will be recruited, for convenience, in three physiotherapy clinics. The study will include three governmental hospitals at Kafr-Elsheikh governorate and El bouhira, comprising desouq general hospital, shubrakhit general hospital, and Pediatric Out-patient Clinic of Faculty of Physical Therapy, Kafr-Elsheikh University.

#### **Sample size calculation:**

Using G-power version 3.1.9.7 for windows and regarding t-test study, alpha level of 0.05, confidence interval 80% and effect size of 1.135 calculated from the previous study of Krishna et al. (43), the total sample size will be 28 children (fourteen in each group), (Figure 1). We will increase number to be 30 children (Fifteen in each group) to avoid any drop out.

To avoid selection bias, the children will be randomly allocated by simple random method via choosing one of two wrapped cards representing the two treatment groups, which are:

- Group (A): will receive virtual reality in addition to the traditional exercise program.
- Group (B): will receive traditional exercise program.

[figure not shown]
[figure not shown]

Figure 1: Sample size calculation in G-power software program.

## **Inclusion criteria:**

Children will be included in the study if they fulfil the following criteria:

1. A medical diagnosis of spastic diplegic CP made by pediatricians or pediatric neurologists.
2. Children with spasticity grades ranged from 1 to 2+ according to Modified Ashworth scale (MAS).
3. Their age range from 6 to 12 years.
4. Children who can sit on the chair with good balance and recognize and follow verbal orders and commands included in both testing and training techniques.

## **Exclusion criteria:**

Children with a permanent spastic diplegia, who might have one or more of the following, will be excluded:

1. They had a permanent deformity (bony or soft tissue contractures).
2. Children having visual or auditory defects.
3. Current hospitalization for urgent medical reasons.
4. Severe mental retardation.
5. Children who will undergo fewer than twelve regular sessions of physical therapy at their place will not be included in the survey.
6. Children with history of epileptic seizure or any diagnosed cardiac or orthopedic disability that may hinder assessment methods and treatment.

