## **Assessment instruments**

1. . Modified Ashworth scale: to measure the degree of spasticity to enroll children in the study, **Appendix I**.

2. Gross Motor Function Measure 88 (GMFM-88) to measure Gross motor performance. **Appendix II.**
3. Pediatric Balance Scale (PBS) to measure Balance. **Appendix III.**
4. Virtual reality glasses (figure 2).
5. Smart display.
6. Spider cage for suspension (figure 3).
7. Smart phone for virtual reality games.

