**Figure 2: virtual reality glasses**

## **Procedure**

### **A. Patients preparation**

1. To start the treatment program, an agreement will be taken from the manager of the outpatient clinics, Faculty of Physical Therapy Kafrelsheikh University.
2. To provide safe and effective treatment, all interventions, evaluation and recording of all measurements at the beginning and at the end of the study will be performed by the primary investigator (the same therapist).
3. All the children parents fitted the inclusion criteria, will be given explanation of the treatment protocol in their understandable language and

they will allow their children to participate after signing a consent form, Appendix IV.

4. All the children demographic and outcome measures data will be collected in especially well-designed sheets, (Appendix V) and (Appendix VI).

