# APPENDICES

## Appendix I

### Modified Ashworth Scale

# MODIFIED ASHWORTH SCALE

| Score | Ashworth Scale (1964)                         | Modified Ashworth Scale Bohannon & Smith (1987)  |
|-------|---|--|
| 0 (0) | No increase in tone                           | No increase in muscle tone   |
| 1 (1) | Slight increase in tone catch when limb moved | Slight increase in muscle tone, manifested by a catch and release or by minimal resistance at the end of the range of motion when the affected part(s) is moved in flexion or extension. |
| 1+(2) |   | Slight increase in muscle tone, manifested by a catch, followed by minimal resistance throughout the remainder (less than half) of the ROM (range of movement).                          |
| 2 (3) | marked increase in tone limb easily flexed    | More marked increase in muscle tone through most of the ROM, but affected part(s) easily moved.  |
| 3 (4) | passive movement difficult                    | Considerable increase in muscle tone passive, movement difficult.  |
| 4 (5) | Limb rigid                                    | Affected part(s) rigid in flexion or extension.  |

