**Appendix V**  
**Demographic Data Sheet**

- **Name:**
- **Age:**
- **Gender:**
- **Diagnosis:**
- **Date of onset:**
- **Type of onset:**
- **Type of CP:**
- **Starting date of physical therapy:**
- **Main problems:**
- **E-mail address:**
- **Telephone number:**

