**Appendix VI**  
**Outcome measures Sheet**

|                        |  |
|------------------------|--|
| • Child name    |  |
| • Serial number |  |

| Outcome measures | Pre-Treatment
Evaluation
Date...../...../..... | Post-Treatment
Evaluation
Date...../...../..... |
|-------------------------|---|--|
| GMFM 88          |   |  |
| PBS              |   |  |

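### Do the undefined therapy-session exclusion and the unlisted spasticity grade 2+ call for a change to the plan?

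*Combined protocol and SAP*

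**What the plan says.** Two eligibility rules in Chapter III are at issue.

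**Exclusion criteria, item 5:** "Children who will undergo fewer than twelve regular sessions of physical therapy at their place will not be included in the survey". No other section defines the sessions, the period or the date of assessment.

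**Inclusion criteria, item 2:** "Children with spasticity grades ranged from 1 to 2+ according to Modified Ashworth scale (MAS". The Assessment instruments section makes the scale in Appendix I the screening tool: "Modified Ashworth scale: to measure the degree of spasticity to enroll children in the study". Appendix I prints grades 0, 1, 1+, 2, 3 and 4. Grade 2 is "More marked increase in muscle tone through most of the ROM, but affected part(s) easily moved", and the next row is grade 3.

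On data capture, the Patients preparation section says "All the children demographic and outcome measures data will be collected in especially well-designed sheets, (Appendix V) and (Appendix VI". Appendix V includes "Starting date of physical therapy" but no session count and no spasticity grade. Appendix VI, the "Outcome measures Sheet", holds the GMFM-88 and PBS scores before and after treatment. Interventions, evaluations and recordings "will be performed by the primary investigator (the same therapist"). The Delimitations section sets three sessions a week for twelve weeks, with assessment of every child before and after treatment. The Statistical analysis section names no analysis set.

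**The concern.** Eligibility should be decidable before a child draws an allocation card. Item 5 is in the future tense and refers to an undefined place, so it could mean earlier usual care, concurrent outside therapy or the trial's own sessions. On the last meaning it becomes an attendance rule applied after allocation. The person applying it could be the therapist who treats the children and scores their outcomes. With no analysis set named, nothing in writing would stop poor attenders being dropped, and in a trial of 30 a few selective removals could shift the result.

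The spasticity limit looks wrong for a simpler reason: the protocol sets a bound that its own instrument does not contain. With three recruiting sites, the bound might be read in different ways. The recorded data would not show this, because neither sheet has a field for the grade.

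**Working it through.** **1. The plan's own figure.** Inputs from the Sample size calculation section: effect size d = 1.135, alpha 0.05, and 80%, which the text calls a confidence interval and is read here as power. For a two-sided two-sample t-test the noncentrality is d × √(n₁n₂/(n₁+n₂)).

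- 13 per group: 1.135 × √6.5 = 2.894, power 0.793.
- 14 per group: 1.135 × √7 = 3.003, power 0.824.

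So 14 per group, 28 in all, reproduces. The increase to 30 leaves room for two losses. Neither eligibility rule enters this calculation.

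**2. Which reading of item 5 fits the text.**

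| Evidence | Child's own therapy | Trial sessions |
|---|---|---|
| Item sits in the exclusion list and speaks of not being included | fits: entry language | fits poorly: no withdrawal language |
| Place is described as the child's | fits | fits poorly: treatment is given by the investigator, with recruitment at hospitals and clinics |
| Appendix V records when physical therapy began | fits | no bearing |
| Delimitations set one full course for all children | no conflict | no attendance threshold is set anywhere |
| Future tense | weak evidence: the protocol uses it throughout | weak evidence |

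On the first reading the rule acts before allocation and applies alike to both future groups. It may change who enters, but it cannot bias the difference between the arms.

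**3. Size on the strained reading.** The course is 3 × 12 = 36 sessions, so the cut-off would be 12/36 = 33%, or 12/3 = 4 weeks of attendance. The documents give no removal rate, so the removals and correlations below are assumptions. Setting: 15 per group, no true effect, two-sided t-test at 0.05, 200,000 simulated trials, the lowest attenders removed from **one arm only**.

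| Correlation of attendance with outcome | 2 removed: shift, false positives | 3 removed: shift, false positives |
|---|---|---|
| 1 (worst case) | 0.23 SD, about 11% | 0.33 SD, about 16% |
| 0.5 | 0.11 SD, 6.3% | 0.16 SD, 7.2% |
| 0.3 | 0.07 SD, 5.3% | 0.10 SD, 5.8% |
| 0 | none, 5.0% | none, 5.0% |

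With the same number removed from both arms, at correlations of 0.3 to 0.5, there is no expected shift and the false-positive rate lies between 5% and 6%.

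Power at d = 1.135 from the smaller sample alone:

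- 15/15: 1.135 × √7.5 = 3.108, power 0.851.
- 15/13: 1.135 × √(195/28) = 2.995, power 0.822.
- 15/12: 1.135 × √(180/27) = 2.931, power 0.804.

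**4. The spasticity bound.** An assessor scoring on Appendix I must choose one of the six printed grades. If 2+ is taken as a point just above 2, then 1, 1+ and 2 lie inside, and 3 and 4 lie outside. No recordable grade falls between 2 and 3, so on this reading the unlisted bound sorts children without ambiguity. It is applied before allocation, so it cannot bias the comparison.

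**5. The data sheets.** Appendices V and VI are described as demographic and outcome sheets, not as a screening log. They also have no dedicated field for seizures, sensory defects, contractures or hospitalisation, all of which are exclusion grounds. A missing field there does not show that a criterion cannot be checked at enrolment.

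**The case for a change.** The best case for acting is that the facts are certain and the remedy is cheap: two reworded criteria, two fields on an existing sheet and a sentence on the analysis set. The trial-session reading of item 5 is less likely but not impossible, and no section says that a randomised child stays in the analysis. A limit of 2+ could also be a slip for another grade, in which case the natural reading admits the wrong range.

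The textual facts stand: item 5 is unspecific, and inclusion item 2 does not match Appendix I. The rest carries less weight. The missing analysis set would remain if item 5 were deleted, so it is a separate matter and does not make item 5 more serious. The plan's stated intention is to collect data on all children in both groups. Divergence between sites is hard to maintain when one therapist makes and records all the measurements, and no separate site screeners are described. A slip in the spasticity grade would change the description of the population but would not bias the comparison.

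**Conclusion.** No change to the plan follows. Item 5 is a gap that the study team would fill sensibly as an entry check on the child's own therapy, and its effect on the randomised comparison is then nil. The 2+ is a mismatch of wording between the Inclusion criteria and Appendix I. It is for the clinical team to reconcile, and nothing here says which grade is intended. Correcting it has no demonstrated effect on any estimate, error rate or sample size.

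This rests on two judgements: that item 5 is entry language, and that assessors record printed grades only. If the first were wrong, the effect at assumed correlations of 0.3 to 0.5, with two or three children removed from one arm, would be a shift of 0.07 to 0.16 SD and a false-positive rate of 5.3% to 7.2%. The 11% and 16% figures need attendance to track outcome perfectly as well as removal from one arm only, and nothing in the documents suggests either.
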